**Table 1 Visit and assessment schedule up to Randomization**

PERIODS	Name / Duration	Screening 4-12 weeks		Run-in 4 weeks			
		1	1.1 	2	3	4	
VISITS 	Number	Week -16 to Week -8	Week -8 at the latest	Week -4	Week -2	End of Run-in	Randomization
	Time	Additional visits as needed		Day -28 (±4 d)	Day -14 (±2 d)	Day -1	Day 1
Informed consent		X					
Eligibility including confirmation of diagnosis of true RHT		X	X	X 	X 	X 	
Demographics / Medical history		X					
Physical examination		X	X	X	X	X	
Concomitant medications		X	X	X	X	X	X
Body weight, height 		X	X	X	X	X 	
12-lead ECG 		X				X 	
Laboratory tests 		X				X 	
Serum pregnancy test		X	X	X		X 	
Urinalysis 						X 	
Urine sampling to monitor treatment adherence 				X 	X	X 	
AOBPM (incl. HR)		X	X	X	X	X	
Home BP monitoring 							
ABPM						X 	X
Blood sampling for biomarkers 		X				X	
Accountability of study treatment and standardized background antihypertensive therapy 				X	X	X 	
Dispensing/return of study treatment and standardized background antihypertensive therapy 			X	X 		X	X
SAE  and AE 		X	X	X	X	X	X

 Unscheduled visits may be performed at any time during the study.  
 Body weight is measured at each visit with the same weight scale. Height is only measured at Screening.  
 ECGs are read centrally.  
 Hematology and clinical chemistry.  
 For UACR determination.

- 
-  Urine sampling at trough (i.e., before intake of study treatment and standardized background antihypertensive therapy). No urine sample to be collected for subjects who do not fulfill Run-in eligibility criteria.
-  Upon investigator's judgment, a home BP monitoring device will be dispensed, if necessary.
-  Blood sampling at trough (i.e., before intake of study treatment and standardized background antihypertensive therapy).
-  Drug accountability (pill counts of study treatment and standardized background antihypertensive therapy).
-  Study treatment including standardized background antihypertensive therapy should be brought back to each visit.
-  All AEs and SAEs that occur after signing the informed consent form and up to 30 days after study treatment discontinuation must be reported.
-  Switch to the standardized background antihypertensive therapy. Visit 1.1 may be at the same day as Visit 1. Additional visits may be performed for further assessments (e.g., to adjust the dose of the standardized background antihypertensive therapy, taking urine samples to monitor adherence).
-  Run-in eligibility criteria.
-  From this time point onwards the dose of the standardized background antihypertensive therapy must be kept stable.
-  Randomization eligibility criteria.
-  For subjects who permanently discontinue prior to Randomization due to any reason or do not fulfill the randomization eligibility criteria, these tests are not mandatory.
-  Two samples will be drawn: one sample for the central laboratory and one sample for the local laboratory to measure hemoglobin, creatinine (to determine eGFR), AST/ALT, and a pregnancy test to confirm eligibility of subjects for randomization.

ABPM = ambulatory blood pressure monitoring; AE = adverse event; ALT = alanine aminotransferase; AOBPM = automated office blood pressure measurement; AST = aspartate aminotransferase; BP = blood pressure; ECG = electrocardiogram; eGFR = estimated glomerular filtration rate; HR = heart rate;; RHT = resistant hypertension; SAE = serious adverse event; UACR = urine albumin-to-creatinine ratio.

**Table 2 Visit and assessment schedule from start of DB treatment period up to EOS**

PERIODS	Name / Duration	DB Treatment 4 weeks			SB Treatment 32 weeks						DB-WD Treatment 12 weeks				FU  30 days		
		Number		5	6	7	8	9	10	11		12	13			14	15
		Time	Week 2	Week 4		Week 6	Week 12	Week 20	Week 28	Week 36		Week 38	Week 40			Week 44	EOT  Week 48
Day 14 (±2 d)	Day 28 (±2 d)		Day 29	Day 42 (±2 d)	Day 84 (±10 d)	Day 140 (±10 d)	Day 196 (±10 d)	Day 252 (±12 d)	Day 253	Day 266 (±4 d)	Day 280 (±4 d)	Day 281	Day 308 (±4 d)	Day 336 (±4 d)	Day 366 (+3 d)		
Physical examination		X	X		X	X	X	X	X		X	X		X	X	X	
Concomitant medications		X	X	X	X	X	X	X	X	X	X	X	X	X	X	X 	
Body weight 		X	X		X	X	X	X	X		X	X		X	X	X	
12-lead ECG 			X		X		X		X					X	X		
Laboratory tests 			X		X	X	X	X	X			X		X	X	X	
Urinalysis 			X			X	X	X	X			X		X	X	X	
Urine sampling to monitor treatment adherence 		X	X		X	X	X	X	X		X	X		X	X		
AOBPM (incl. HR)		X	X		X	X	X	X	X		X	X		X	X	X	
Home BP monitoring 		→															
ABPM			X	X					X	X		X	X				
Blood sampling for PK 			X														
Blood sampling for biomarkers 			X				X		X			X					
Accountability of study treatment and standardized background antihypertensive therapy 		X	X		X	X	X	X	X		X	X		X	X	X	
Dispensing/return of study treatment and standardized background antihypertensive therapy			X	X		X	X	X	X	X		X	X	X	X	X	
SAE  and AE 		X	X	X	X	X	X	X	X	X	X	X	X	X	X	X 	

 Unscheduled visits may be performed at any time during the study.

 Body weight is measured at each visit with the same weight scale.

 ECGs are read centrally.

 Hematology and clinical chemistry including NT-proBNP and serum pregnancy test. During SB aprocitentan part, urine pregnancy tests will be performed monthly (i.e., between scheduled visits) at home with kits that are provided to the subject.

 For UACR determination.

 Urine sampling at trough (i.e., before intake of study treatment and standardized background antihypertensive therapy).

 Upon investigator's judgment, a home BP monitoring device will be dispensed, if necessary.

 Blood sampling at trough (i.e., before intake of study treatment and standardized background antihypertensive therapy).

 Study treatment including standardized background antihypertensive therapy should be brought back at each visit for drug accountability (pill counts).

 All AEs and SAEs that occur after signing the informed consent form and up to 30 days after study treatment discontinuation must be reported.

 Randomized subjects who prematurely discontinue prior to Week 48/Visit 15 should have an EOT visit scheduled no later than 7 days after the last dose of randomized study treatment.

 For subjects who discontinued during the RI period, this will be a phone call to collect adverse events and concomitant medications only.

ABPM = ambulatory blood pressure monitoring; AE = adverse event; AOBPM = automated office blood pressure measurement; BP = blood pressure; DB = double-blind; ECG = electrocardiogram; EOS = End-of-Study; EOT = End-of-Treatment; FU = follow-up; HR = heart rate; NT-proBNP = N-terminal pro-brain natriuretic peptide; PK = pharmacokinetic(s); RI = run-in; SAE = serious adverse event; SB = single-blind; UACR = urine albumin-to-creatinine ratio; WD = withdrawal.

## 2.3 Overview of analysis periods

The RI period starts at the date of the first dose of RI treatment and ends at the date of the last dose of RI treatment.

The randomized treatment period is divided into three parts: DB, SB aprocitentan and DB-WD. The DB (SB, DB-WD, respectively) part starts at the DB (SB, DB-WD, respectively) treatment start date and ends at the DB (SB, DB-WD, respectively) treatment end date (collected on the Study Treatment Log).

In some analyses the DB and SB aprocitentan parts are combined, indicated as ‘DB+SB part’. For details see Section 10.1.1.

## 2.4 Impact of the COVID-19 pandemic

Idorsia provided instructions and guidance in line with Health Authority guidelines (FDA, EMA and individual national health authorities) released in March 2020. These recommendations and instructions are summarized in an addendum of the protocol [D-20.063]. The impact on the statistical analysis is addressed in Sections 2.4, 5.1.2, 5.1.3, 5.2, 6.2.7, 6.3.7, 6.5.1 and 6.5.2 of this SAP.

# 3 OBJECTIVES

## 3.1 Primary objective

The primary objective of the study is to demonstrate the BP lowering effect of aprocitentan when added to standard-of-care in subjects with true RHT.

## 3.2 Secondary objectives

The secondary objectives of the study are:

- To demonstrate that the effect of aprocitentan on BP is durable when added to standard-of-care in subjects with true RHT.
- To evaluate the long-term safety and tolerability of aprocitentan in subjects with true RHT during 48 weeks of treatment.

## 3.3 Other objectives

- Evaluate steady-state trough plasma concentrations of aprocitentan after 4 weeks of treatment.
- Evaluate the endothelin system activity and the effect of aprocitentan on micro- and macro-vascular complications based on specific biomarkers.

## 4 ANALYSIS SETS

### 4.1 Definitions of analysis sets

#### 4.1.1 Screened set

The SCR includes all subjects who have given informed consent to participate in the study and have a subject number.

#### 4.1.2 Run-in set

The RIS includes all subjects from the SCR who received at least one dose of placebo in the RI period.

#### 4.1.3 All-randomized set

The RND includes all subjects who were randomized.

#### 4.1.4 Full analysis set

The FAS includes all subjects who were randomized and have a baseline SiSBP, measured by AOBPM at trough. Subjects will be evaluated according to their assigned study treatment in the DB part: aprocitentan 25 mg, aprocitentan 12.5 mg or placebo.

#### 4.1.5 Modified Full analysis set

The mFAS includes all subjects from the FAS who were re-randomized in the DB-WD part of the study and who have a DB-WD baseline SiSBP, measured by AOBPM at trough. Subjects will be evaluated according to their assigned study treatment in the DB-WD part: aprocitentan 25 mg or placebo.

#### 4.1.6 Per-protocol analysis set

The PPS includes all subjects from the FAS without protocol deviations that potentially affect the primary endpoint. Reasons for exclusion from the PPS are:

- DB treatment duration less than 21 days.
- Use of at least one medication as per protocol deviation list code 04A04 and 04A07 or use of additional diuretic or rescue medication in DB part.
- Compliance with DB treatment < 80% or > 120% [as calculated in Section 5.5.2].
- Compliance with standardized background antihypertensive therapy in DB part < 80% or > 120% [as calculated in Section 5.5.2].

The purpose of the PPS is to enable a supportive analysis of the DB part.

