#### 4.1.7 Modified Per-protocol analysis set

The mPPS includes all subjects from the mFAS without protocol deviations that potentially affect the key secondary endpoint. Reasons for exclusion from the mPPS are:

- DB-WD treatment duration less than 21 days.
- Use of at least one medication as per protocol deviation list code 04A05 and 04A08 or use of additional diuretic or rescue medication in DB-WD part 3.
- Compliance with DB-WD treatment < 80% or > 120% [as calculated in Section 5.5.2].
- Compliance with standardized background antihypertensive therapy in DB-WD part < 80% or > 120% [as calculated in Section 5.5.2].

The purpose of the mPPS is to enable a supportive analysis of the DB-WD part.

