#### 4.1.13 Pharmacokinetic set

The PK set includes all subjects from the SAF who received at least one dose of aprocitentan, had evaluable plasma concentrations and did not violate the protocol in a way that might affect the evaluation of the PK endpoint.

Reasons for exclusion from the PK set are:

- DB treatment duration less than 21 days.
- Compliance with DB treatment < 80% or > 120% [as calculated in Section 5.5.2].
- AOBPM not done at trough at Week 4 (V6) as per protocol deviation list code 03F20.
- PK samples not collected at Week 4 (V6) as per protocol deviation list code 03F26.

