## 6.2 Primary endpoint analysis

### 6.2.1 Variable

The primary efficacy endpoint is the change from baseline to Week 4 of DB treatment in mean trough SiSBP measured by AOBPM.

Here 'mean trough' denotes the average of four AOBPM readings (from a Microlife® WatchBP Office device performing five readings; the first is excluded from the average which will be in the vendor's data transfer) taken at trough (i.e., before the morning intake of study treatment and standardized background antihypertensive therapy).

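### The per-protocol sets do not exclude an AOBPM taken off trough at Week 4 (PPS) or Week 40 (mPPS), although the SAP uses the Week 4 deviation to exclude subjects from the PK set

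*SAP*

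**What the plan says.** SAP Section 6.2.1 makes timing part of the primary variable. The SiSBP value is the mean of four AOBPM readings "taken at trough (i.e., before the morning intake of study treatment and standardized background antihypertensive therapy". The key secondary variable in Section 6.3.1 is also a trough value, at Week 40.

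Section 4.1.6 states the principle of the PPS: it takes FAS subjects "without protocol deviations that potentially affect the primary endpoint". It then gives four reasons for exclusion:

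- short exposure ("DB treatment duration less than 21 days");
- medication under deviation codes 04A04 and 04A07, or an added diuretic or rescue medication;
- compliance with double-blind treatment outside 80–120%;
- compliance with background therapy outside 80–120%.

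Section 4.1.7 builds the mPPS in the same way, from mFAS subjects "without protocol deviations that potentially affect the key secondary endpoint", with four parallel reasons for the withdrawal part.

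Section 4.1.13 lists among the reasons for leaving the PK set: "AOBPM not done at trough at Week 4 (V6) as per protocol deviation list code 03F20".

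**The concern.** A per-protocol set should remove subjects whose data do not measure the endpoint as the protocol defines it. A Week 4 reading taken after the morning tablets is not a trough reading, so on the SAP's own principle it is a deviation that can affect the primary endpoint. The list nevertheless keeps such a subject in the blood pressure analysis, while the same blood pressure deviation removes the subject from the concentration analysis. SAP Version 3 revised the definitions of the PPS, mPPS and PK set (Section 14.1), and neither that log nor Section 11 gives a reason for the different treatment.

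At stake is what the per-protocol analysis can be said to confirm. If off-trough readings remain, it does not isolate the trough effect in subjects who followed the protocol. A decision on which readings count as per protocol, taken after unblinding, would be open to challenge.

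**Working it through.** **Step 1. Which rule covers off-trough timing, and at which visit?**

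| SAP section | Baseline / DB-WD baseline | Week 4 / Week 40 |
|---|---|---|
| 4.1.4 FAS, 4.1.5 mFAS | trough required | no condition |
| 4.1.6 PPS, 4.1.7 mPPS | inherited from FAS / mFAS | no condition |
| 4.1.13 PK set | not applicable | Week 4: excluded under 03F20 |

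The gap is therefore confined to the Week 4 and Week 40 readings.

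**Step 2. Is the list operative or only illustrative?** Section 5.3 tabulates exclusions from the PPS and mPPS by the reasons in Sections 4.1.6 and 4.1.7. A programmer would build the sets from those lists.

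**Step 3. Does another written rule remove the reading?**

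- Section 6.2.2 keeps AOBPM values whatever the intercurrent event. Timing is not among the intercurrent events, so this rule neither removes nor protects an off-trough value.
- Section 6.2.4 drops values after treatment discontinuation, an added diuretic or rescue medication, in one sensitivity analysis only. It does not mention timing.
- Section 10.1.2 chooses among values by closeness to the planned date, the latest time on the same day, and on- or off-treatment status. The indicator planned for AOBPM records is on-treatment, not trough. If a subject had both a trough and a later reading on one day, the rule would select the later one.

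No rule sets an off-trough value to missing.

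**Step 4. Size.** The plan gives no figure to reproduce. Let *f*<sub>A</sub> and *f*<sub>P</sub> be the shares of PPS subjects off trough at Week 4 in an aprocitentan arm and in placebo, and *d*<sub>A</sub> and *d*<sub>P</sub> the mean post-dose minus trough SiSBP in those arms. Then approximately

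bias in the difference vs placebo = *f*<sub>A</sub>·*d*<sub>A</sub> − *f*<sub>P</sub>·*d*<sub>P</sub>.

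None of the four inputs is in the documents. All values below are assumptions, and results are absolute sizes:

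- Equal shares and equal *d*: 5% × 10 − 5% × 10 = 0 mmHg.
- Shares of 5% and 3%, common *d* of 10 mmHg: (0.05 − 0.03) × 10 = 0.2 mmHg.
- 5% in one arm and none in the other, *d* of 10 mmHg: 0.05 × 10 = 0.5 mmHg.
- Equal share *f*, with *d* differing between arms by 2 to 10 mmHg: from 0.01 × 2 = 0.02 mmHg at *f* = 1% to 0.10 × 10 = 1.0 mmHg at *f* = 10%.

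**The case against.** The strongest reply is that the variable is itself defined as a trough value. A post-dose reading would then fail the definition in every analysis set, and the PPS would need no separate rule. This is a fair reading of Section 6.2.1. However, no derivation rule carries it out, and Section 10.1.2, where such a rule would stand, selects values without checking trough. Two programmers could reasonably differ. The objection turns the gap into one that a clarification could also close, but it does not remove it.

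Second, the PK exclusion has its own purpose, because Section 6.7 analyses trough concentrations. That is true, so its presence there does not by itself prove an inconsistency. It does show that the deviation is identified and coded for Week 4.

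Third, part 1 is double-blind, and nothing in the documents suggests that off-trough visits would be more frequent in one arm. This stands, and it argues for a small effect. With equal shares, bias would still arise if the post-dose change differed between active treatment and placebo.

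Fourth, Section 5.2 summarises all protocol deviations by treatment group, so the deviation falls within that reporting. That gives some transparency but does not change who is analysed.

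Two stronger readings are tempting. A reader might infer that baseline timing is also unprotected; Sections 4.1.4 and 4.1.5 already secure it. A reader might also infer that the acute effect of the triple background therapy biases the comparison; all arms take it, so at equal frequency it cancels.

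**Conclusion.** The gap is real and narrow. As written, the PPS list does not carry out its own principle for the Week 4 reading, and the mPPS list does not for Week 40. Only the supportive per-protocol analyses are affected.

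A reader might infer that the confirmatory result is at risk. The documents do not support that: H10 and H20 are tested on the FAS and H30 on the mFAS, and neither set depends on the per-protocol lists. How an off-trough reading is treated in those main analyses is a separate question, which this point does not settle.

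The size cannot be established. Under the assumed ranges the bias in the difference runs from zero to about 1.0 mmHg; the upper end needs 10% of subjects off trough and a 10 mmHg difference between arms in the post-dose change. It would also be wrong to take share times difference in one arm as the bias whenever shares differ: with a common post-dose change, only the difference in shares counts.

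Two limits apply. The deviation code list was not supplied, so neither the frequency of 03F20 nor the existence of a Week 40 code can be checked. Protocol Version 3 was not supplied either, only its COVID-19 addendum, so any protocol rule on off-trough visits cannot be seen.

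**What to change.** In Section 4.1.6, add a fifth reason for exclusion: Week 4 (Visit 6) AOBPM not done at trough, deviation code 03F20. State that it applies to all three arms. This matters because the PK set contains only subjects who received aprocitentan, so its use of the code cannot be carried over unchanged.

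In Section 4.1.7, add the corresponding deviation at Week 40 (Visit 13). Take it from the deviation list if a code exists; otherwise derive it from the recorded AOBPM and dose times.

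If the intention is instead that off-trough readings are set to missing, or deliberately kept, the SAP should say so and give the reason.

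The cost is one bullet in each section, a derivation for Week 40 if no code exists, and a slightly smaller PPS and mPPS. The Section 5.3 tables would then report the number excluded for this reason by arm. The change should be made before unblinding.

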#### 4.1.7 Modified Per-protocol analysis set

The mPPS includes all subjects from the mFAS without protocol deviations that potentially affect the key secondary endpoint. Reasons for exclusion from the mPPS are:

- DB-WD treatment duration less than 21 days.
- Use of at least one medication as per protocol deviation list code 04A05 and 04A08 or use of additional diuretic or rescue medication in DB-WD part 3.
- Compliance with DB-WD treatment < 80% or > 120% [as calculated in Section 5.5.2].
- Compliance with standardized background antihypertensive therapy in DB-WD part < 80% or > 120% [as calculated in Section 5.5.2].

The purpose of the mPPS is to enable a supportive analysis of the DB-WD part.

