**Figure 1 Study design**

EOT = End-of-Treatment; FU = follow-up; V = visit.

The randomized treatment period lasts for 48 weeks [until EOT, as displayed in Figure 1]. The purpose of this period is to evaluate the primary and secondary objectives of the study. This period consists of three sequential parts:

- In the first DB part of 4 weeks, subjects will be randomized to aprocitentan 25 mg, aprocitentan 12.5 mg or placebo in a 1:1:1 ratio.
- In the second SB part of 32 weeks, all subjects will receive aprocitentan 25 mg.
- In the third DB-WD part of 12 weeks, subjects will be re-randomized at Week 36 to aprocitentan 25 mg or placebo in a 1:1 ratio.

The EOT visit will take place at Week 48 (i.e., end of DB-WD part) or earlier in the event of premature discontinuation of study treatment.

Approximately 4000 subjects were expected to be screened in order to enroll approximately 1500 subjects with a diagnosis of RHT into the SB placebo RI period. At least 600 subjects were to be randomized and at least 380 subjects were expected to be re-randomized in the DB-WD part. At least 300 subjects were expected to complete the study (including the 30-day safety FU period). The study was to be conducted at approximately 100 sites in approximately 20 countries.

The sponsor planned to look at the drop-out rate (between Randomization and Re-randomization) nine months after the randomization of the 200th subject.

If the observed drop-out rate was such that the expected number of subjects to be re-randomized in the DB-WD part was less than 380, the number of subjects randomized could have been increased to maintain at least 85% power for the DB-WD part (which is

achieved when 324 subjects are re-randomized). It appeared that the drop-out rate was lower than expected, so no sample size increase was needed to compensate for drop-out.

Ultimately, 730 subjects were randomized. The overrunning was caused by the addition of sites and countries in 2020 meant to compensate for the lower recruitment due to the Covid-19 pandemic. In order to give these new sites a reasonable chance to contribute to the study, the timelines were prolonged, which, combined with a surge in screening when the EOS was announced, lead to an over-recruitment. The study was finally conducted at 193 sites in 22 countries.

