## 5.5 Study treatment duration and compliance

### 5.5.1 Treatment duration

Randomized treatment duration (in days) is defined separately for the DB, SB aprocitentan and DB-WD parts as the date of the last dose of treatment in the DB (SB aprocitentan, DB-WD, respectively) part minus the date of the first dose in the DB (SB aprocitentan, DB-WD, respectively) part plus one day, ignoring treatment interruptions. The detailed derivations based on the **Study Treatment Log** are given in Section 10.1.1. Randomized treatment duration will also be expressed in weeks.

RI treatment duration is defined as the date of the last dose of SB placebo minus the date of the first dose of SB placebo plus one day [see Section 10.1.1].

Standardized background antihypertensive therapy duration in the RI period as well as in the DB, SB aprocitentan, and DB-WD parts is defined similarly based on the **Standardized Background Antihypertensive Therapy Log**.

Treatment duration (in days as well as weeks) will be summarized by study part and treatment group (within study part) in the SAF, rSAF and mSAF, respectively. Total exposure (in subject-years, where a year equals 365.25 days) will also be summarized by study part and treatment group.

Time from first dose of DB treatment to (premature) treatment discontinuation in the DB or SB aprocitentan part will be summarized by treatment group using Kaplan-Meier plots (supplemented with a table displaying the numbers of subjects at risk, with an event, and censored by treatment group, using weekly intervals) in the SAF. For subjects who completed the treatment, time to discontinuation will be censored at the last dose of SB treatment (or at the last dose of DB treatment if the subject did not enter the SB part). Additionally, a ‘two-step’ Cox model with a factor for treatment in the DB part will be fitted. This model allows for different treatment effects in the DB and SB aprocitentan parts. The treatment effect in the latter part (if any) is expected to be smaller than in the former part [for details, see Section 8.2].

Time from first dose of DB-WD treatment to (premature) treatment discontinuation in the DB-WD part will be summarized similarly in the mSAF, except that the Cox model is the conventional one.

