### 5.5.2 Compliance with study treatment

Randomized treatment compliance is defined separately for the DB, SB aprocitentan and DB-WD parts as:

$$\text{Compliance} = \frac{[(\text{number of tablets dispensed} - \text{number of tablets returned}^*) / \text{treatment duration [days]}]}{1}$$

\* If a subject did not return his/her bottle (e.g., the bottle is lost), the compliance will not be calculated and the compliance for the parts will be set to missing. The bottle is allocated to the study part in which it was dispensed.

Here the number of tablets is calculated separately for the DB (SB aprocitentan, DB-WD, respectively) part based on the **Study Treatment Dispensing & Accountability** eCRF and the DB (SB aprocitentan, DB-WD, respectively) treatment duration is defined as in Section 5.5.1.

RI treatment compliance is defined as the number of tablets taken during the RI period according to the **Study Treatment Dispensing & Accountability** eCRF, divided by the RI treatment duration (in days) defined in Section 5.5.1.

Standardized background antihypertensive therapy compliance is defined similarly based on the **Standardized Background Antihypertensive Therapy Dispensing & Accountability** eCRF.

Randomized treatment compliance will be summarized by study part and treatment group (within study part) in the SAF, rSAF and mSAF, respectively. RI treatment compliance will be summarized based on the RIS.

Compliance to the standardized antihypertensive background therapy will be summarized by study part and treatment group (within study part) in the SAF, rSAF and mSAF, respectively.

*Adherence* (Y/N) to the standardized background antihypertensive therapy (as measured by urinalysis for valsartan) will be summarized by study part, visit and treatment group (both within study part) in the SAF, rSAF and mSAF, respectively.

A subject is considered to have interrupted study treatment or standardized background antihypertensive therapy if on the **Study Treatment Log or Background Therapy Log** the ‘Reason for treatment stop’ is ‘Interruption due to an AE’ or ‘Interruption not due to an AE’.

Reasons for study treatment interruption will be summarized by study part and treatment group (within study part) in the SAF, rSAF or mSAF, where appropriate.

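### The modified per-protocol set judges rescue, diuretic use and compliance over the 12-week withdrawal part, but its only specified analysis ends at Week 40

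*SAP*

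**What the plan says.** SAP 4.1.7 takes the mPPS from mFAS subjects "without protocol deviations that potentially affect the key secondary endpoint". SAP 6.3.1 defines that endpoint as the SiSBP change from DB-WD baseline (Week 36) to Week 40. The exclusion reasons include:

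- fewer than 21 days of DB-WD treatment;
- medications under deviation codes 04A05 and 04A08, or "use of additional diuretic or rescue medication in DB-WD part 3";
- compliance below 80% or above 120%, once for study treatment and once for background therapy, in the DB-WD part.

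The length of that part is given in SAP 2.1: "In the third DB-WD part of 12 weeks, subjects will be re-randomized at Week 36". SAP 10.1.1 runs it to the DB-WD treatment stop date. SAP 5.5.2 gives one compliance ratio per part: "Randomized treatment compliance is defined separately for the DB, SB aprocitentan and DB-WD parts as" tablets dispensed minus tablets returned, over treatment duration. SAP 5.5.1 takes duration as "the date of the last dose of treatment in the DB (SB aprocitentan, DB-WD, respectively) part minus the date of the first dose", plus one day. Background therapy is handled in the same way.

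The only analysis specified on the mPPS is the key secondary mixed model (SAP 6.3.5), which Table 4 lists with Weeks 38 and 40. The Week 44 and Week 48 models are on the mFAS. Section 4.1.7 also states a broader aim: "The purpose of the mPPS is to enable a supportive analysis of the DB-WD part".

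**The concern.** The inclusion sentence and the exclusion criteria work to different time horizons. A diuretic started at Week 44, or tablets missed in Week 46, cannot change a blood pressure taken at Week 40. Both can still remove that reading from the analysis. In the other direction, poor intake before Week 40 can be hidden by good intake afterwards.

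The likely source is wording carried over from the per-protocol set for the first part. There, SAP 4.1.6 excludes for "use of additional diuretic or rescue medication in DB part", and the study design says "In the first DB part of 4 weeks". That part ends at its own endpoint, so the wording fits. It does not fit a part that continues eight weeks past the endpoint.

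Two things are at stake. The mPPS is the only key secondary analysis that filters on compliance, so a reader will take it as the effect in subjects who adhered up to Week 40. And if rescue after Week 40 is prompted by the Week 40 blood pressure, exclusion depends on the outcome and, through it, on the arm.

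**Working it through.** The SAP gives no figure for the size or result of the mPPS, so there is none to reproduce. The check applies its own definitions.

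**Inputs.** Re-randomization at Week 36, Week 40 target WD day 28, Week 48 target WD day 84 (Table 6). Visit tolerance ±4 days at Weeks 40 and 48 (Table 2). Compliance limits 80% and 120% (4.1.7). One tablet per day, which the formula in 5.5.2 implies by dividing tablets by days.

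**Share of the period after the endpoint.** 84 − 28 = 56 days, and 56/84 = 67%.

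**Compliance threshold for a completer.** 0.80 × 84 = 67.2. So 68/84 = 81.0% is kept and 67/84 = 79.8% is excluded.

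**Full intake to Week 40, then excluded.** 28 + 39 = 67, so 28/28 followed by 39/56 (70%) or less is excluded. On the upper limit, 28/28 followed by 73 tablets in 56 days gives 101/84 = 120.2%, also excluded.

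**Low intake to Week 40, then kept.** The least intake to Week 40 is 68 minus the later tablets:

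| Later intake | Least intake to Week 40 that is kept |
|---|---|
| 48/56 | 20/28 = 71% |
| 50/56 | 18/28 = 64% |
| 53/56 | 15/28 = 54% |
| 56/56 | 12/28 = 43% |

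The last row is an extreme. With the visit tolerances it runs from 7/24 = 29% (Week 40 on day 24, Week 48 on day 88) to 16/32 = 50% (day 32 and day 80).

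**Mixed horizons within the set.** The 21-day rule is 21/28 = 75% of the time to Week 40 and equals the lower bound of the Week 40 window in Table 6, but it is only 21/84 = 25% of the part. A subject who stops on day 29 meets it and is judged on 29 days of intake. A fully adherent completer who first adds a diuretic at Week 44 is out.

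**Selection effect (illustration only).** The documents give no effect size, SD, later-rescue rate or link between rescue and blood pressure, so all are assumed. Take a true difference of 5 mmHg, an SD of 14, rescue after Week 40 in 5%, 10% or 20% of placebo subjects, and a logistic dependence on the Week 40 change. The difference among subjects kept is:

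| OR per 10 mmHg | 5% | 10% | 20% |
|---|---|---|---|
| 1.0 | 4.99 | 4.98 | 5.02 |
| 1.5 | 4.95 | 4.87 | 4.79 |
| 2.0 | 4.85 | 4.70 | 4.52 |

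At OR 2.0 the shrinkage is 3%, 6% and 9.6%; for example (5 − 4.52)/5 = 9.6%. The OR 1.0 row differs from 5 only by simulation error.

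A fuller version adjusts for baseline, with difference 5–6 mmHg, SD 13–15 and later rescue in 2–10% of the aprocitentan arm. With no rescue before Week 40 it gives 0% at OR 1.0, 0.2–1.7% at 1.35, 1.4–7.4% at 2.0 and 2.6–11.9% at 2.7. If 5% with early rescue, also driven by Week 40 blood pressure, are removed first, the range at OR 2.7 is 2.2–9.9%. The shift is toward zero because more placebo subjects with high Week 40 values are removed.

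**The case against.** **The set may be meant for the whole part.** The purpose sentence refers to the DB-WD part, Table 3 lists the mPPS against DB-WD AOBPM endpoints in general, and compliance is computed once per part throughout the SAP. A part-level adherence set is a legitimate choice. But no mPPS analysis past Week 40 is specified, the inclusion sentence names the Week 40 endpoint, and a 21-day minimum does not define adherence over 84 days. One Week 40 SiDBP row in Table 4 reads mFAS where the parallel DB row reads PPS; even if mPPS was meant, it too ends at Week 40.

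**The consequence is small and the bias is assumed.** This stands. SAP 6.3.4 already has a hypothetical-strategy analysis that handles rescue by timing and keeps a Week 40 value taken before later rescue. No odds ratio in the illustration has support in the documents, the top of the range needs several unfavourable assumptions together, and the compliance cases show only what is possible.

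**Readings that go too far.** A reader might infer that the key secondary result is compromised. It is not: H30 is tested on the mFAS. A reader might infer that the set flatters the drug; the modelled shift is toward no effect. A reader might infer that every mPPS criterion is misaligned. The 21-day rule fits Week 40, and the content and period of codes 04A05 and 04A08 are not given, so nothing can be said about them.

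**Conclusion.** The point holds as a minor error in the plan as written, not merely a missing detail. Following 4.1.7 literally discards valid Week 40 readings because of later events and lets later intake decide whether earlier intake counts as adequate. This contradicts the section's own inclusion principle.

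The compliance figures follow from the SAP, given one tablet per day and visits on target days. How many subjects are affected cannot be derived. The effect on the estimate is a loss of precision only if later rescue is unrelated to Week 40 blood pressure. If it is related, the estimate shrinks by roughly 0–12% over the range tried (up to about 0.6–0.7 mmHg on a difference of 5–6 mmHg), which rests wholly on outside assumptions. The scope is one supportive analysis.

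**What to change.** 1. **Diuretic/rescue clause (4.1.7).** Count use from re-randomization up to the Week 40 AOBPM used in the analysis or, if there is none, up to WD day 28, the Table 6 target. A default date is needed because SAP 6.3.2 expects 10% of the mFAS to lack a Week 40 AOBPM. This edit stands on its own and costs almost nothing.
2. **Compliance (4.1.7 and 5.5.2).** If Week 40 pill counts are in the database, apply the 80–120% limits, for study treatment and background therapy, from the first DB-WD dose to the day before the Week 40 AOBPM inclusive. Use WD day 28 if there is no Week 40 AOBPM, or the last dose if earlier. The day before is the right end because trough readings precede that morning's dose, and one day is 1/28 = 3.6%, enough to cross a limit. For a bottle still in use, take the Week 40 visit count. If that count is missing, set compliance to missing, do not exclude on this criterion, and report the number. Do not substitute the Week 38 count, which says nothing about the two weeks before the endpoint.
3. **If interim counts were not recorded**, keep whole-part compliance and state that it does not describe intake to Week 40. Table 2 schedules accountability at Weeks 38 and 40, but 5.5.2 uses only tablets dispensed and returned, so this must be checked first.
4. **Whole-part criteria.** Keep them only for a named mPPS analysis to Week 48, if one is wanted.

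Cost: three edited criteria, one derivation, a little programming and some missing Week 40 compliance values. The change should be fixed before unblinding.
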